5.2.2 Secondary Endpoints

• Time to disease progression

- Tolerability (type, frequency, severity and relationship of adverse events to study treatment based on the NCI criteria)
- Duration of response from the start of therapy
- Overall survival
- Serum cytokine levels
- Tumor Control Rate

Investigational Plan

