Response rate (overall and complete) in non-target lesions following local radiation with concurrent lenalidomide in patients previously refractory to the combination of lenalidomide and rituximab.

STUDY DESIGN:

The study will be a multi-institution, phase II clinical trial in patients with previously untreated indolent Non-Hodgkin's lymphoma. Patients will receive lenalidomide 20 mg daily, on days 1-21 of a 28 day cycle. Rituximab 375 mg/m2 will be administered weekly for 4 doses starting day 15 of cycle 1, to be repeated if patient does not achieve a complete response after cycle 4, on days 1, 8, 15 and 22 of cycle 5. Therapy with lenalidomide may be discontinued after twelve cycles if the patient achieves a complete response.

Patients progressing on lenalidomide and rituximab will be offered treatment in a radiotherapy cohort. Patients will continue lenalidomide at the current dose, on days 1-21 of a 28 day cycle. Local fractionated radiotherapy will be delivered to a single site of disease days 1-5 of a 28 day

cycle to 20 Gy in 4 Gy fractions. Re-staging will be performed every 2 months, and lenalidomide will be continued until disease progression or intolerance.

STUDY ENDPOINTS:

Primary:

Complete response (CR), near complete response (CRu), or partial response (PR), stable disease (SD) of 4 months.

Secondary:

Time to disease progression, tolerability, duration of response, overall survival, and tumor control rate from the start of treatment.

Measurement of immune profile

STUDY DURATION:	TOTAL SAMPLE SIZE:
Patients will be enrolled over 2yrs.	Approximately 30 patients
	Of the 30 total patients 10 progressing patients will be offered optional treatment on the radiotherapy arm
DOSING REGIMEN(S):	STUDY DRUG SUPPLIES:
Lenalidomide will be initiated at 20 mg daily, days 1-21 of a 28 day cycle, to be continued until disease progression, unacceptable toxicity or after twelve cycles if the patient has achieved a complete response. Rituximab 375 mg/m2/wk x 4 weeks, to begin Day 15 of cycle 1. After 4 cycles of therapy if patient	Celgene Corporation will supply lenalidomide as 5 mg capsules.
does not achieve CR, the patient will receive a second course of Rituximab.	
Blood samples for companion study to assess immune profiles will be obtained within 1 week	
prior to starting treatment & then on days 15, 30,	
60 and 120, and then at the end of treatment or	

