8.6 Progressive disease (PD) in PR patients or nonresponders

- ≥50 % increase from nadir in the SPD of any previously identified abnormal node for PRs or nonresponders.
- Appearance of any new lesion during or at the end of therapy.

Summary of response criteria:

Response	Definition			
Category		Nodal Mass	Spleen, Liver	Bone Marrow
Category				
CR	Disappearance of all evidence of disease	(a) FDG-avid or PET positive prior to therapy; mass of any size permitted if PET negative (b) Variably FDG-avid or PET negative; regression to normal size on CT	Not palpable, nodules disappeared	Infiltrate cleared on repeat biopsy; if indeterminate by morphology, immunohistochemistry should be negative
PR	Regression of measurable disease and no new sites	≥ 50% decrease in SPD of up to 6 largest dominant masses; no increase in size of other nodes (a) FDG-avid or PET positive prior to therapy; one or more PET positive at previously involved site (b) Variably FDG-avid or PET negative; regression on CT	≥50% decrease in SPD of nodules (for single nodule in greates transverse diameter); no increase in size of liver or spleen	Irrelevant
SD	Failure to attain CR/PR or PD	(a) FDG-avid or PET positive prior to therapy; PET positive at prior sites of disease and no new sites on CT or PET		

Response Category	Definition	Nodal Mass	Spleen, Liver	Bone Marrow
		(b) Variably FDG-avid or PET negative; no change in size of previous lesions on CT		
Relapse/PD	Any new lesion or increase by _≥ 50% of previously involved sites from nadir	Appearance of a new lesion(s) >1.5 cm in any axis, ≥ 50% increase in SPD of more than one node, Or ≥ 50% increase in longest diameter of a previously identified node >1 cm in short axis Lesions PET positive if FDG-avid lymphoma or PET positive	> 50 increase from nadir in the SPD of any previous lesions	New or recurrent involvement

8.7 Duration of Overall Response:

The duration of overall response is measured from the time measurement criteria are met for CR/PR (whichever status is recorded first) until the first date that recurrent or progressive disease is objectively documented (taking as reference for progressive disease the smallest measurements recorded since the treatment started).

The duration of overall complete response is measured from the time measurement criteria are first met for CR until the first date that recurrent disease is objectively documented.

8.7.1 Duration of Stable Disease:

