Stable disease is measured from the start of the treatment until the criteria for disease progression are met, taking as reference the smallest measurements recorded since the treatment started.

The clinical relevance of the duration of SD varies for different tumor types and grades. Therefore, it is highly recommended that the protocol specify the minimal time interval required between two measurements for determination of SD. This time interval should take into account the expected clinical benefit that such a status may bring to the population under study.

8.7.2 Time to Progression:

Time to progression will be measured as the time from when the patient started treatment to the time the patient is first recorded as having disease progression, or the date of death if the patient dies due to causes other than disease progression.

8.7.3 Time to Treatment Failure:

Time to treatment failure will be measured as the time from when the patient started treatment to the time the patient is withdrawn due to: adverse events, progressive disease/insufficient therapeutic response, death, failure to return, and refused treatment/did not cooperate/withdrew consent. The date of last dose of treatment will be used as the date of event in the case that PD was not recorded earlier.

8.7.4 Survival:

Survival will be measured as the time from start of treatment to the date of death or the last date the patient was known to be alive.

9 **Data Management**

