11.2 Datasets to be analyzed

The primary study endpoint is response to therapy (defined as a CR, nCR, or PR of 4 months). The secondary end points (time to progression, tolerability, duration of response and overall survival will be measured from the time of entry into the clinical trial.

Toxicity information recorded will include the type, severity, time of onset, time of resolution, and the probable association with the study regimen. Tables will be constructed to summarize the observed incidence by severity and type of toxicity.

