11.3 Statistical Methodology

30 patients will be treated with rituximab and lenalidomide at indicated dose levels. Objective response (CR +PR) will be monitored using Simon's optimal 2-stage design. This study design is optimal in that sense that it minimizes the expected sample size among competing designs. The OR rate of rituximab naïve follicular lymphoma patients treated with rituximab alone is approximately 60%. A 20% increase in the objective response rate with the addition of lenalidomide to 80% in this treatment naïve patient population would justify evaluation of this regimen in larger, more definitive trials. We assume a one-sided type I error rate of 5% and desire at least 80% power to conclude that this regimen elicits and objective response rate significantly greater than 60% if the true response rate of this regimen is 60% or higher. Under these assumptions, if 11 or fewer OR's are observed in the first 26 patients, the principal investigator may conclude that regimen is insufficiently active to warrant further study. Otherwise, accrual will continue to a total of 30 patients. If 15 or more OR's are observed in 30 patients, this regimen will be deemed sufficiently active to warrant further study. Given the relatively small sample size the additional study in patients receiving radiation therapy would be considered exploratory. Any documented response would be considered "significant" and warrant further study.

Analysis Plan:

Continuous variables (e.g., age, hematology values) will be summarized using the mean (s.d.) or median (range). Frequency tables will be used to summarize categorical variables. Logistic regression will be used to assess the impact of patient characteristics (e.g., low/high LDH) on the objective response rate. The distribution of time-to-event endpoints (e.g., CR duration, overall survival) will be estimated using the method of Kaplan and Meier. Comparison of time-to-event endpoints by important subgroups of patients will be made using the logrank test. Cox (proportional hazards) regression will be used to evaluate multivariable predictive models of time-to-event outcomes.

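### Duration of response is started at start of therapy (5.2.2), at trial entry (11.2) and at first documented CR/PR (8.7), and nothing says which governs

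*Combined protocol and SAP*

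**What the plan says.** Three sections of the combined protocol and SAP give duration of response a starting point.

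- **Section 5.2.2 (Secondary Endpoints):** "Duration of response from the start of therapy". No end is given.
- **Section 11.2 (Datasets to be analyzed):** a list that begins with time to progression and tolerability ends "duration of response and overall survival will be measured from the time of entry into the clinical trial". Entry is not defined, and no end is given.
- **Section 8.7 (Duration of Overall Response):** "measured from the time measurement criteria are met for CR/PR (whichever status is recorded first"), running "until the first date that recurrent or progressive disease is objectively documented". The same section starts duration of complete response when CR criteria are first met.

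The synopsis lists "duration of response, overall survival, and tumor control rate from the start of treatment". The closing phrase may apply to the whole list or only to tumor control rate.

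For analysis, Section 11.3 says: "The distribution of time-to-event endpoints (e.g., CR duration, overall survival) will be estimated using the method of Kaplan and Meier". It gives no time origin. Section 8.7.2 adds: "Time to progression will be measured as the time from when the patient started treatment". Section 8.7.4 also starts survival at the start of treatment.

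**The concern.** Duration of response should describe how long a response lasts once it exists. Under 5.2.2 or 11.2 the clock runs while the patient has not yet responded, so a slow responder gains duration by being slow. In a responder who progresses, the result is the time to progression again, and two of the listed secondary endpoints carry the same information.

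The same data therefore give different reported durations depending on which section the analyst follows, and each choice could be defended as following the protocol. The choice could also be made after the data are seen. Duration of response is a named secondary objective in Section 5.1.2, so the figure will be reported.

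**Working it through.** The plan states no figure for this point, so there is none to reproduce. The check compares the definitions and then sizes the gap from the schedule.

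**Definitions side by side**

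| Source | Start | End |
|---|---|---|
| 5.2.2, duration of response | start of therapy | not given |
| 11.2, duration of response | trial entry | not given |
| 8.7, duration of response | first documented CR or PR | documented recurrence or progression |
| 8.7.2, time to progression | start of treatment | first recorded progression, or certain deaths |

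No section ranks these, cross-refers between them for this endpoint, or labels one as a sensitivity analysis.

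**Overlap with time to progression.** Let T0 be treatment start, R the date of first documented response and P the date of progression. Sections 5.2.2 and 11.2 give no end, so the end in 8.7 is used for all three.

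- Under 8.7: P − R.
- Under 5.2.2: P − T0, which is time to progression under 8.7.2.
- Under 11.2: P − T0 plus the interval from entry to treatment start.
- Difference, 5.2.2 minus 8.7: (P − T0) − (P − R) = R − T0, the time to first documented response.

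**Size of R − T0 at scheduled scans**

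Inputs: 28-day cycles (Section 6.1); response assessed after every 2 cycles (Section 2, footnote 7); a visit window of ±3 days after cycle 1 (Section 2). No cycle delays are assumed, and months are days divided by 30.44.

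| First documented at | Days | With ±3 days | Months |
|---|---|---|---|
| First scan (after cycle 2) | 2 × 28 = 56 | 53 to 59 | 56 / 30.44 = 1.8 |
| Second scan (after cycle 4) | 4 × 28 = 112 | 109 to 115 | 112 / 30.44 = 3.7 |
| Third scan (after cycle 6) | 6 × 28 = 168 | 165 to 171 | 168 / 30.44 = 5.5 |

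The third row is possible because a second rituximab course is given in cycle 5 to patients without CR after cycle 4.

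**Addition under 11.2**

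- *Entry as registration:* Appendix VII allows registration up to 72 hours before treatment, so 0 to 3 days. The first-scan gap becomes 53 to 59 + 3 = 62 days.
- *Entry as consent at the start of screening:* Section 5.4 links signing consent to study entry and allows 28 days for screening, so up to about 28 days. The first-scan gap becomes 53 to about 59 + 28 = 87 days.

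The same addition applies to time to progression and survival, which 11.2 starts at entry and 8.7.2 and 8.7.4 start at treatment start.

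**The case against.** The best defence is that 8.7 governs in practice. It alone is operational: it has a start, an end and a reference measurement. Section 11.3 names CR duration, which only 8.7 defines. By contrast, 5.2.2 is a bullet in a list. The sentence in 11.2 stands under a heading about datasets and includes tolerability, which has no time-to-event origin, so it could be read as saying when data collection begins. This makes 8.7 the likely choice, but not the stated one. The endpoint list attaches an origin to this endpoint specifically, and the statistical section gives a measurement rule that names it.

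It is also fair to say that the stakes are limited. The trial is single-arm with 30 patients, duration of response has no hypothesis or threshold, and any of the versions can be computed later from the dates collected. That limits the weight of the point without removing the conflict.

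A reader might infer more than the documents support:

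- *That the synopsis is a further conflicting definition.* Its closing phrase can belong to tumor control rate alone.
- *That the reported median shifts by a fixed amount or percentage.* The gap is each patient's own time to response, and the documents give no response duration in untreated indolent disease from which to form a percentage.
- *That the handling of deaths is a further error.* Section 8.7 ends only at recurrence or progression, and making death an event would change what is estimated. Section 8.7.2 adds "or the date of death if the patient dies due to causes other than disease progression"; its natural reading is that a lymphoma death is itself progression.
- *That only responses confirmed under footnote 7 may count.* Section 8.7 does not say so.

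The last two are optional questions for the sponsor, not part of this point.

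**Conclusion.** The point holds. Duration of response has three stated origins with no order of precedence. The practical conflict is 8.7 against 5.2.2 and 11.2.

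Measured by 5.2.2 rather than 8.7, a responder's duration is longer by 56 days (53 to 59) when response is first documented at the first scheduled scan, by 112 days (109 to 115) at the second, and by more for later responses. Section 11.2 adds up to 3 or up to about 28 days, depending on what entry means. These figures assume scans on schedule, no cycle delays and the end point of 8.7 throughout.

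The effect is confined to descriptive secondary endpoints. A reader might infer that the trial's conclusion is at risk. It is not on this account, because neither the primary response analysis nor the two-stage rule uses any duration. The wording should still be settled before analysis, because two of the three rules as written do not measure how long a response lasts.

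**What to change.** - **Sections 5.2.2 and 11.2:** state that duration of response runs from first documented CR or PR, as defined in 8.7.
- **Synopsis:** use the same wording, for clarity.
- **Section 11.2:** start time to progression and survival at the start of treatment, to match 8.7.2 and 8.7.4.

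The cost is a few lines of wording. No new data are needed, because treatment start and assessment dates are already collected. The one downside is that the reported duration of response will be shorter than under 5.2.2 or 11.2, by each responder's time to first documented response (plus, for 11.2, the interval from entry to treatment).

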5.3 Overall design

The study is a phase II clinical trial with all patients to be accrued at UCD Cancer Center and other participating centers. All patients who are eligible will receive both lenalidomide and rituximab.

- Lenalidomide will be started at 20 mg daily, days 1-21 of a 28 day cycle.
- A total of 30 patients will be evaluated in this study.
- Rituximab 375 mg/m2/wk x 4 weeks, to begin on day 15 of cycle 1. After 4 cycles of therapy if a patient has not achieved a CR, the patient will be given a second course of Rituximab, on days 1, 8, 15 and 22 of cycle 5.

Patients who progress through this combination will be offered optional participation in a radiotherapy cohort. Up to 10 patients who consent will continue lenalidomide and receive local radiotherapy to a single target lesion.

- Lenalidomide will be continued at the patient's most recent dose daily, days 1 21 of a 28 day cycle.
- Radiotherapy will be delivered to a single involved site to a dose of 20 Gy over 5 daily fractions of 4 Gy each, day 1-5, using electron or photon beams with a conventional linear accelerator.

Investigational Drugs

5.3.1 DESCRIPTION of lenalidomide

REVLIMID® (lenalidomide), a thalidomide analogue, is an immunomodulatory agent with anti-angiogenic properties. The chemical name is 3-(4-amino-1-oxo 1,3-dihydro -2*H*-isoindol-2-yl) piperidine-2,6-dione and it has the following chemical structure:

Chemical Structure of Lenalidomide

3-(4-amino-1-oxo 1,3-dihydro-2*H*-isoindol-2-yl) piperidine-2,6-dione

The empirical formula for lenalidomide is $C_{13}H_{13}N_3O_3$, and the gram molecular weight is 259.3.

Lenalidomide is an off-white to pale-yellow solid powder. It is soluble in organic solvent/water mixtures, and buffered aqueous solvents. Lenalidomide is more soluble in organic solvents and low pH solutions. Solubility was significantly lower in less acidic buffers, ranging from about 0.4 to 0.5 mg/ml. Lenalidomide has an asymmetric carbon atom and can exist as the optically active forms S(-) and R(+), and is produced as a racemic mixture with a net optical rotation of zero.

REVLIMID[®] (lenalidomide) is available in 5 mg and 25 mg capsules for oral administration. Each capsule contains lenalidomide as the active ingredient and the following inactive ingredients: lactose anhydrous, microcrystalline cellulose, croscarmellose sodium, and magnesium stearate.

5.3.1.1 CLINICAL PHARMACOLOGY

Mechanism of Action:

The mechanism of action of lenalidomide remains to be fully characterized. Lenalidomide possesses immunomodulatory and antiangiogenic properties. Lenalidomide inhibited the secretion of pro-inflammatory cytokines and increased the secretion of anti-inflammatory cytokines from peripheral blood mononuclear cells. Lenalidomide inhibited cell proliferation with varying effectiveness (IC50s) in some but not all cell lines. Of cell lines tested, lenalidomide was effective in inhibiting growth of Namalwa cells (a human B cell lymphoma cell line with a deletion of one chromosome 5) but was much less effective in inhibiting growth of KG-1 cells (human myeloblastic cell line, also with a deletion of one chromosome 5) and other cell lines without chromosome 5 deletions. Lenalidomide inhibited the expression of cyclooxygenase-2 (COX-2) but not COX-1 in vitro.

5.3.1.2 Pharmacokinetics and Drug Metabolism:

Absorption:

Lenalidomide, in healthy volunteers, is rapidly absorbed following oral administration with maximum plasma concentrations occurring between 0.625 and 1.5 hours post-dose. Co-administration with food does not alter the extent of absorption (AUC) but does reduce the maximal plasma concentration (Cmax) by 36%. The pharmacokinetic disposition of lenalidomide is linear. Cmax and AUC increase proportionately with increases in dose. Multiple dosing at the recommended dose-regimen does not result in drug accumulation.

Pharmacokinetic sampling in myelodysplastic syndrome (MDS) patients was not performed. In multiple myeloma patients maximum plasma concentrations occurred between 0.5 and 4.0 hours post-dose both on Days 1 and 28. AUC and Cmax values increase proportionally with dose following single and multiple doses. Exposure (AUC) in multiple myeloma patients is 57% higher than in healthy male volunteers.

Pharmacokinetic Parameters:

Distribution:

In vitro (14C)-lenalidomide binding to plasma proteins is approximately 30%.

Metabolism and Excretion:

The metabolic profile of lenalidomide in humans has not been studied. In healthy volunteers, approximately two-thirds of lenalidomide is eliminated unchanged through urinary excretion. The process exceeds the glomerular filtration rate and therefore is partially or entirely active. Half-life of elimination is approximately 3 hours.

5.3.1.3 Supplier(s)

Celgene Corporation will supply Revlimid®, lenalidomide to study participants at no charge through Celgene's Revlimid Risk Evaluation and Mitigation Strategy[™] (REMS) (formerly known as RevAssist® Program).

5.3.1.4 Dosage form

Lenalidomide will be supplied as 5 mg capsules for oral administration.

5.3.1.5 Packaging

Lenalidomide will be shipped directly to patients or to the clinic site for IND studies. Bottles will contain a sufficient number of capsules for one cycle of dosing.

5.3.1.6 Labeling

Lenalidomide investigational supplies are dispensed to the patients in individual bottles of capsules. Each bottle will identify the contents as study medication and bear Celgene's name, quantity contained, and the standard caution statement as follows: Caution: New drug - Limited by Federal law to investigational use.

The study drug label must be clearly visible. For appropriate drug accountability, it is recommended that each bottle be marked with the institutional or Celgene protocol number (RV-NHL-PI-0448) upon receipt. Additional labels must not cover the Celgene label. Additional labels must not cover the Celgene label.

5.3.1.7 Receipt of study drug

The Investigator or designee is responsible for taking an inventory of each shipment of study drug received, and comparing it with the accompanying study drug accountability form. The Investigator will verify the accuracy of the information on the form, sign and date it, retain a copy in the study file, and return a copy to Celgene or its representative.

